prospective, randomized, double-blind placebo controlled study. The study is designed to evaluate the efficacy, safety, and tolerability of transdermal patch of Rotigotine (RTG) versus placebo (PLC) as add-on therapy with AChEI in patients with mild AD according to the consensus diagnostic criteria and MMSE score of ≥18 and ≤24 at screening. Two groups of patients with mild AD will be involved (50 patients each). One group will be assigned to treatment with RTG 4 mg and the other one to PLC as add on to AChEI therapy. Clinical and neurophysiological measurements will be collected before and after drug administration.

120 SECTION 3. ABBREVIATIONS AND DEFINITIONS

- 121 **A** β : amyloid- β peptides
- 122 **AChEI:** acetylcholinesterase inhibitor
- 123 **AD:** Alzheimer's disease
- 124 ADAS-Cog: Alzheimer's Disease Assessment Scale—Cognitive subscale
- 125 ADCS-ADL: Alzheimer's Disease Cooperative Study–Activities of Daily Living Inventory
- **ADDF:** Alzheimer's Drug Discovery Foundation
- 127 AE: adverse event: Any untoward medical occurrence in a patient or clinical investigation subject
- administered a pharmaceutical product that does not necessarily have a causal relationship with this
- treatment. An adverse event can therefore be any unfavorable and unintended sign (including an abnormal
- laboratory finding), symptom, or disease temporally associated with the use of a medicinal (investigational)
- product, whether or not related to the medicinal (investigational) product.
- 132 **ANOVA:** analysis of variance
- 133 **APOE:** apolipoprotein E
- 134 Blinding: A procedure in which one or more parties to the trial are kept unaware of the treatment
- assignment(s). Blinding will remain in effect until final database lock. A double-blind study is one in which
- neither the patient nor any of the investigator who are involved in the treatment or clinical evaluation of the
- subjects are aware of the treatment received.
- 138 **CDR:** Clinical Dementia Rating Scale
- 139 CRF: Case report form, a printed or electronic form for recording study patients' data during a clinical
- study, as required by the protocol.
- 141 **CSF:** cerebrospinal fluid
- 142 DA: dopamine
- 143 **EEG:** electroencephalogram
- 144 Efficacy: Efficacy is the ability of a treatment to achieve a beneficial intended result under controlled
- 145 conditions.
- End of study (trial): The date of the last visit or last scheduled procedure shown in the Study. Schedule for

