5.1. Primary Objective

The primary objective of this study is to test the hypothesis that therapy with Rotigotine could have a relevant clinical impact on cognitive impairment in Alzheimer's disease patients as compared with placebo. The primary objective will be evaluated using a study endpoint at 24 weeks after initiation of treatment. The primary objective will be assessed using a Generalized Linear Mixed Model (GLMM) for repeated measures on the primary outcome: Alzheimer's Disease Assessment Scale-Cognitive (ADAS-Cog), in which the specific hypothesis is that the cognitive decline at the end of the treatment phase for RTG will be significantly less than that for placebo.

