6.4. Evaluation Phase

- During the week before starting RTG/PLC administration, and during the week at the end of 24-week
- treatment, AD patients will undergo clinical assessment and neurophysiological assessment in two different
- 330 days.

318

319

320

321

322

323

324

325

326

327

340

- 1) Clinical Assessment: before and after the 24 weeks of treatment the ADAS-Cog, ADCS-ADL,
- FAB and NPI will be administered.
- 2) Neurophysiological assessment: for EEG-TMS recordings, a TMS-compatible EEG equipment
- will be used for recording EEG activity from the scalp (BrainAmp 32MRplus, BrainProducts). The
- 335 EEG will be continuously acquired from 32 scalp sites positioned according to the 10-20
- International System. TMS-EEG recordings will be performed over the left prefrontal cortex (PFC)
- and left parietal cortex (I-PPC). To precisely position the coil over the cortical sites across different
- sessions, a neuronavigation system (Softaxic, E.M.S.) will be used. During the TMS-EEG session,
- each cortical site will be stimulated with 80 single TMS pulses (ISI: 0.3 Hz) (Koch et al., 2018).

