2. STATISTICAL ANALYSIS PLAN

2.1. Determination of Sample Size

A total of 94 randomly assigned patients (47 per group) were planned on the basis of our previous study in which we assessed the effects of rotigotine on cortical plasticity and cognitive functions in a small sample of Alzheimer's disease patients (Koch et al., 2014). In that pilot study, a significant (although unpowered) difference was observed in pre-post (12 weeks) treatment with rotigotine in n=7 patients in both the cognitive measures MMSE (mean pre=21.73, SD=4.14; mean post=23.23, SD=3.93) and in FAB (mean pre=10.85, SD=4.43; mean post=12.32, SD=4.48). Treatment duration of the present study is twice larger than the one of the pilot study thus a larger effect size is expected. However, for precautionary reasons, we consider the same effect sizes found in the previous work (equal to 0.48 for MMSE and equal to 0.42 for FAB computed as post-pre means over standard deviation of difference post-pre), for the sample size calculation of the present study. In detail, adopting a two-tailed paired t-test, with type I error alpha=0.05 and a plausible correlation between pre-post measured variables of 0.7, the FAB effect size equal to 0.42 requires a minimum sample of n=46 for reaching a power of 0.8. For MMSE, this sample size allows to reach a power of 0.9. The minimum total sample size was then augmented up to N=92 considering the matched placebo group.

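### The stated power of 0.80 (FAB) and 0.90 (MMSE) belongs to a one-arm pre-post test, not to the rotigotine–placebo comparison of ADAS-Cog change that is the trial's primary question

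*Combined protocol and SAP*

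**What the plan says.** SAP section 2.1 takes its effects from a 12-week pilot in which seven patients received rotigotine. It quotes pilot means and SDs for MMSE and for "FAB (mean pre=10.85, SD=4.43; mean post=12.32, SD=4.48", and standardised effects "equal to 0.48 for MMSE and equal to 0.42 for FAB computed as post-pre means over standard deviation of difference post-pre". It then sizes the trial by "adopting a two-tailed paired t-test, with type I error alpha=0.05 and a plausible correlation between pre-post measured variables of 0.7". The FAB effect leads to n=46 for power 0.8, and the same n is said to give 0.9 for MMSE. The placebo arm enters only at the end: "The minimum total sample size was then augmented up to N=92 considering the matched placebo group". The same section opens with a different total: "A total of 94 randomly assigned patients (47 per group) were planned". The protocol summary has a third: "Two groups of patients with mild AD will be involved (50 patients each". Section 6.1 agrees with the third, at approximately 100.

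The primary hypothesis, in protocol section 5.1, is that "cognitive decline at the end of the treatment phase for RTG will be significantly less than that for placebo". Section 9.1 names ADAS-Cog change to week 24 as the primary measure, and section 9.2 lists FAB as secondary. The clinical scales are given twice: "before and after the 24 weeks of treatment the ADAS-Cog, ADCS-ADL", with FAB and NPI completing the list. SAP section 2.3.4 tests the treatment effect in a mixed model with group, time and their interaction. MMSE is absent from sections 9.1, 9.2 and 6.4, although section 2.3.4 does name a model on it.

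**The concern.** A paired t-test on one arm asks whether patients on rotigotine differ from their own baseline. The trial asks whether they change differently from patients on placebo. Adding a second arm of the same size does not carry the power of the first question over to the second, because the difference between two independent mean changes has twice the variance of one of them.

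The endpoint differs as well. The calculation rests on a secondary scale and on one that is not a listed outcome, and section 2.1 has no ADAS-Cog input. Anyone who reads 0.80 as the power of the primary test attributes to the design a property that has not been shown. That matters most if the primary result is not significant and its meaning has to be judged.

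**Working it through.** **Inputs.** From SAP section 2.1: pilot means and SDs, r=0.7, two-sided alpha 0.05, effects 0.42 and 0.48 in units of the SD of change, n=46, totals 92 and 94. From the protocol summary: 50 per arm. From section 6.1: 1:1 allocation.

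**1. The plan's effect sizes.** d = (post − pre) / √(s₁² + s₂² − 2·r·s₁·s₂).

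- FAB: 1.47 / √(19.625 + 20.070 − 27.785) = 1.47 / 3.451 = 0.426.
- MMSE: 1.50 / √(17.140 + 15.445 − 22.778) = 1.50 / 3.131 = 0.479.

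Both agree with the stated 0.42 and 0.48.

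**2. The plan's power.** Paired t-test, noncentrality d√n, n − 1 degrees of freedom. At n=46 and d=0.42, noncentrality is 0.42 × √46 = 2.85 and power is 0.796. At d=0.48 it is 3.26 and power is 0.890. The n that solves for 80% at 0.42 is 46.5. The stated figures reproduce to rounding for the test named.

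**3. The same effect between arms.** With two assessments, the group-by-time test is essentially a comparison of mean change between arms. Write σ for the SD of change. The variance of one arm's mean change is σ²/n, and that of the difference between arms is 2σ²/n. Noncentrality therefore becomes d√(n/2), with 2n − 2 degrees of freedom. With d as the between-arm difference, which means zero mean change on placebo:

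| n per arm | noncentrality at 0.42 | power at 0.42 | power at 0.48 | difference with 80% power (SD of change) |
|---|---|---|---|---|
| 46 | 2.01 | 0.513 | 0.625 | 0.590 |
| 47 | 2.04 | 0.522 | 0.634 | 0.584 |
| 50 | 2.10 | 0.548 | 0.661 | 0.566 |

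For scale, 80% power at a difference of 0.42 would take 90 per arm.

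**4. Sensitivity to placebo change.** 47 per arm, a gain of 0.42 SD on rotigotine, placebo change assumed:

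| assumed placebo change (SD of change) | between-arm difference | power |
|---|---|---|
| gain of 0.10 | 0.32 | 0.34 |
| none | 0.42 | 0.52 |
| decline of 0.10 | 0.52 | 0.70 |
| decline of 0.18 | 0.60 | 0.82 |

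**5. The pilot's significance.** On a paired t-test with n=7, t = d√7 with 6 degrees of freedom. MMSE: 0.479 × 2.646 = 1.27, p=0.25. FAB: 0.426 × 2.646 = 1.13, p=0.30. Section 2.1 nevertheless describes the pilot differences as significant. On that test, significance would need d of at least 2.447/√7 = 0.92, and so a correlation of about 0.92 (MMSE) or 0.94 (FAB) instead of 0.7.

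**The case against.** The strongest reply is that zero change on placebo is not what the protocol expects. Section 5.1 speaks of decline, and section 9.1 cites 8–9 ADAS-Cog points a year, which over 24 weeks is 8 × 24/52 = 3.7 to 9 × 24/52 = 4.2 points. If the SD of change were 5–7 points (an assumption, since the documents give none), that is a placebo decline of 3.7/7 = 0.53 to 4.2/5 = 0.83 SD. Added to a 0.42 SD gain on rotigotine, it would put power above 99% at 47 per arm. This stands as a warning against treating 51–52% as the answer. It does not rescue the stated 0.80, which uses no placebo change at all. Nor do the documents show that the cited rate applies to mild patients already on a cholinesterase inhibitor.

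It is also fair to say that the arithmetic in section 2.1 is right for the test it names. The fault is the choice of test and endpoint.

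A reader might go further in four ways that the documents do not support:

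- That the primary test has 51–52% power. This carries a FAB effect to another scale and fixes placebo change at zero.
- That the trial can detect only the abolition of most of the expected decline. This needs an ADAS-Cog SD that is not given, and it treats no change on rotigotine as a ceiling, whereas the planned effect is an improvement.
- That 92 against 94 is a 2% attrition allowance. Section 2.1 calls 92 a minimum, section 6.1 says about 100, and neither gap is described as attrition.
- That the pilot was not significant. Its actual test and correlation are not shown. Only the mismatch within section 2.1 is established.

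Adjusting for baseline ADAS-Cog could raise power, but section 2.3.4 specifies adjustment for age and education only, so no such gain is credited here.

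**Conclusion.** The point holds as a mismatch of test and endpoint. The 0.80 and 0.90 are correct for a within-arm change in FAB and MMSE, and they say nothing about the rotigotine–placebo difference in ADAS-Cog change. Power for that comparison cannot be computed from the documents.

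The plan's own 0.42, read as a between-arm difference with no placebo change, gives 51–55% over the three stated arm sizes, and 0.48 gives 62–66%. Over the assumed placebo changes tabulated above, power at 47 per arm runs from 34% to 82%. All of this assumes two-sided alpha 0.05, a comparison of change scores, equal SDs in the two arms, and the stated numbers all evaluable. Losses would lower it. The three totals, and the conflict between the claimed pilot significance and effects built on r=0.7, are smaller faults in the same section.

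**What to change.** Rewrite SAP section 2.1 for the between-arm difference in week-24 ADAS-Cog change under the planned group-by-time analysis. State the assumed difference, the SD of change and the assumed placebo change, each with its source. Replace the 0.80 and 0.90 with what the fixed N delivers, for example:

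> With 46–47 evaluable patients per arm, the trial has 80% power for a between-arm difference of 0.58–0.59 SD of change. Power for a difference of 0.42 SD is 51–52%.

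Add a short table of power against placebo change.

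State one target N, with any attrition allowance made explicit, in section 2.1, the protocol summary and section 6.1. Either take the pilot effect sizes from its actual paired differences and name the test used, or remove the word significant. Say whether MMSE is an outcome, so that sections 9.1, 9.2, 6.4 and 2.3.4 agree.

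The cost is wording in the SAP and protocol, with no extra patients. The drawback is that the stated power will look less favourable.

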6.1. Summary of Study Design

This is a 24-week, randomized, double-blind, placebo-controlled, Phase 2 study, comparing Rotigotine (Neupro, UCB pharma) with placebo for 24 weeks in approximately 100 patients with mild AD, defined as having a Visit 1 MMSE score of 18 to 26. Patients will be adaptively randomized (Lin et al. 2016) in a 1:1 ratio stratified by sex, age, APOE genotype, education and screening severity (MMSE) to one of the following treatment groups: Placebo group; RTG 4mg group. All patients started the treatment with a package containing 7 patches of RTG 2mg/placebo, and continued treatment with 6 packages, each one containing 30 patches of RTG 4mg/placebo depending on the arm of randomization. The primary hypothesis being tested is that Rotigotine will slow the cognitive and functional decline of AD as compared with placebo in patients with mild AD.

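### SAP 2.1 plans 94 randomised patients, the protocol plans about 100, and neither figure is tied to the calculated minimum of 46 per arm by an allowance for loss

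*Combined protocol and SAP*

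**What the plan says.** Two places in the protocol give the planned size. The synopsis says: "Two groups of patients with mild AD will be involved (50 patients each"). Section 6.1 describes a comparison "for 24 weeks in approximately 100 patients with mild AD".

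SAP 2.1 opens with a different planned size: "A total of 94 randomly assigned patients (47 per group) were planned on the basis of our previous study". It then sets out the calculation, "adopting a two-tailed paired t-test, with type I error alpha=0.05 and a plausible correlation between pre-post measured variables of 0.7", and concludes that "the FAB effect size equal to 0.42 requires a minimum sample of n=46 for reaching a power of 0.8". It closes with the doubled figure: "The minimum total sample size was then augmented up to N=92 considering the matched placebo group".

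Under protocol 6.2 and 6.4, the efficacy scales are given before treatment and at the end of the 24 weeks, with no efficacy assessment in between. SAP 2.3.2 expects that some patients will be excluded from analysis sets, since reasons for exclusion are to be reported. The documents give no dropout rate, no inflation factor, and no rule for when randomisation ends.

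**The concern.** The planned number randomised decides when recruitment closes, and readers use it later to judge whether the trial ran as designed. With 94 in the SAP and 100 in the protocol, a stop at either figure could be reported as the plan.

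The second issue is what the figures leave for loss. A paired pre-post test needs both measurements, so the minimum of 46 per arm counts patients who reach week 24. A planned number randomised should exceed that minimum by an explicit allowance. Neither 94 nor 100 is presented that way. The mixed model does not remove the problem: with only two time points, a patient without a week-24 visit contributes a baseline value but nothing on change.

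**Working it through.** **Inputs (all from SAP 2.1 unless noted).** FAB before treatment: mean 10.85, SD 4.43. FAB after: mean 12.32, SD 4.48. Assumed correlation 0.7. Stated effect sizes 0.42 (FAB) and 0.48 (MMSE). Two-sided alpha 0.05, target power 0.80, stated minimum 46 per arm. Planned sizes: 94 (SAP 2.1) and 100 (protocol synopsis and 6.1). Allocation 1:1 (protocol 6.1).

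**1. Reproduce the plan's figure.**

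SD of the FAB change = √(4.43² + 4.48² − 2 × 0.7 × 4.43 × 4.48) = √(19.625 + 20.070 − 27.785) = √11.910 = 3.451.

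d = (12.32 − 10.85) / 3.451 = 1.47 / 3.451 = 0.426, printed in the SAP as 0.42.

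Power of the paired t-test comes from the noncentral t distribution with n − 1 degrees of freedom and noncentrality d√n. At d = 0.426, power is 0.798 for n = 45 and 0.807 for n = 46. So 46 is the smallest n that reaches 0.80, and 2 × 46 = 92. The plan's minimum is reproduced. For MMSE, d = 0.48 and n = 46 give 0.890, in line with the stated 0.9.

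**2. Loss that still leaves 46 per arm.** Margin per arm = N/2 − 46.

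| Planned N | Per arm | Losses allowed per arm | As a share |
|---|---|---|---|
| 94 (SAP 2.1) | 47 | 47 − 46 = 1 | 1/47 = 2.1% |
| 100 (protocol) | 50 | 50 − 46 = 4 | 4/50 = 8.0% |

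**3. Power on the plan's own FAB calculation.** The documents give no loss rate, so 10% and 20% are assumptions. Completers are rounded down: 47 × 0.9 = 42.3, 50 × 0.9 = 45, 47 × 0.8 = 37.6, 50 × 0.8 = 40.

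| Loss to week 24 | N = 94: completers per arm, power | N = 100: completers per arm, power | Difference |
|---|---|---|---|
| none | 47, 0.805 | 50, 0.829 | 0.024 |
| 10% (assumed) | 42, 0.757 | 45, 0.787 | 0.030 |
| 20% (assumed) | 37, 0.701 | 40, 0.736 | 0.035 |

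These use the printed d = 0.42. At the unrounded 0.426, the 10% row becomes 0.769 and 0.798.

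**4. What would keep 46 evaluable per arm.** Required n per arm = 46 / (1 − loss), rounded up. At 5% loss, 46/0.95 = 48.4, so 49 per arm, 98 in total. At 8%, 46/0.92 = 50, so 100. At 10%, 46/0.90 = 51.1, so 52 per arm, 104 in total. At 20%, 46/0.80 = 57.5, so 58 per arm, 116 in total. The protocol's 100 is thus consistent with an allowance of up to 8%, but the documents do not say that this is where it comes from.

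**The case against.** The best defence is that the figures are close and that one of them is qualified. Section 6.1 says approximately 100, and 94 is 6% below that. This has some force against 6.1 alone. It does not reconcile the synopsis, which gives 50 per group without qualification, with the SAP, which gives 47 per group, also without qualification.

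Three stronger readings are tempting, and the documents do not support them.

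- A reader might count 92 as a third enrolment target and picture a team stopping there with no margin. SAP 2.1 calls 92 a minimum and names 94 in the same section as the number planned. A floor of 92 and a plan of 94 do not contradict each other, and a minimum has no margin over itself by definition.
- A reader might conclude that the stopping point is undefined. It is inconsistent: each part of the document does state a size.
- A reader who puts the printed 0.42 into a paired t-test gets power 0.796 at n = 46 and might call the 46 wrong. That is rounding. The pilot figures give 0.426, at which 46 suffices.

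It is also fair to object that the power figures concern a within-arm FAB test, while the primary analysis is a between-group mixed model on ADAS-Cog (protocol 5.1, SAP 2.3.4). That objection stands. The figures show only how the two planned sizes relate to the plan's own stated minimum.

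**Conclusion.** The point holds as an inconsistency between two planned sizes, 94 and about 100, with neither linked to the evaluable minimum of 46 per arm. At 94 there is room for one loss per arm; at 100 there is room for four. The choice between them is worth 2.4 power points with no loss and about 3 points at an assumed 10% loss, on the plan's own FAB calculation. At 10% loss, 94 falls clearly short of 0.80 (0.76 to 0.77), and 100 lands at or just under it (0.79 to 0.80, depending on rounding of the effect size). At an assumed 20% loss both fall short (about 0.70 and 0.74).

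The effect is modest. The loss margins rest only on the documents' figures; the power under loss also rests on assumed rates. Nothing here shows that 46, 47 or 50 per arm is adequate for the ADAS-Cog comparison. It should be corrected because planned size is a basic design figure and the correction is cheap.

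**What to change.** State one randomised N throughout. The simplest route is to replace the 94 (47 per group) in SAP 2.1 with the protocol's 100 (50 per group). Then describe 46 per arm (92 in total) as the minimum number with both baseline and week-24 data, and say that 100 allows 8% loss to week 24. If 94 is the true target, change the synopsis and 6.1 to 94 and state that the quoted power assumes no more than about 2% loss. On either route, state the expected loss with its basis, give the power at that loss, and label the quoted power as belonging to the within-arm FAB calculation.

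The cost is a few sentences in SAP 2.1 or two in the protocol. Choosing 100 needs no patients beyond the number the protocol already states. The one downside is that the stated power looks slightly less favourable once loss is included.

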2.2. Method of Assignment to Treatment

Subjects who meet all criteria for enrollment will be randomized to double-blind treatment. Randomization will be performed and assigned independently by a statistician working in an independent institution, held centrally, and not divulged to any other person involved in the trial until after database lock. In order to obtain homogeneous and balance study groups in terms of age, sex and APOE carriers, an adaptive randomization will be adopted; more specifically, a covariate-adaptive randomization will be performed, i.e. a randomization procedure that uses past group assignments and subject covariate values to select the probability of future group assignments, with the objective to balance group assignments within covariate profiles (Lin et al. 2016). The simple

randomization procedure could lead to unbalanced groups (with respect to specific key patients features) when the sample size is relatively small: the adaptive procedure allowed to overcome this drawback through a pseudo-random assignment that took into account the key features (age [55-70 vs >70], sex [male vs female] and APOE [carriers vs non-carriers]) of the subjects previously assigned into the study groups.

